4 STUDY OBJECTIVES AND ENDPOINTS

4.1 Objectives

4.1.1 Primary Objectives

- To evaluate the rate of hematologic improvement of the eltrombopag/lenalidomide combination (as per Modified IWG criteria)
- To evaluate the safety and tolerability of the combination

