6.1 Inclusion Criteria

Subjects must meet the following inclusion/exclusion criteria to be eligible for the study.

- 1 Age \geq 18 years.
2. Patient must have a documented diagnosis of MDS according to World Health Organization (WHO) criteria (see Appendix IV) or non-proliferative chronic myelomonocytic leukemia (CMML) (WBC \leq 12,000/uL).
3. Patients must have International Prognostic Scoring System (IPSS) categories of Low- or Intermediate-1-risk disease (see Appendix 4).
4. Patients must have symptomatic anemia untransfused with hemoglobin \leq 10.0g/dL within 8 weeks of registration or with RBC transfusion-dependence (i.e., \geq 2 units/month) confirmed for a minimum of 8 weeks before randomization. Or patients have platelet $<$ 50,000/uL with hemoglobin $>$ 10.0 g/dL.
5. Patients must have IPSS score determined by cytogenetic analysis prior to randomization. Patients with cytogenetic failure and \leq 10% marrow blasts will be eligible.
6. Patients must be off all disease modifying therapy for MDS for 28 days prior to initiation of study treatment. Patients may receive hydrocortisone prophylactically to prevent transfusion reactions.
7. Patients must not have documented iron deficiency. All patients must have documented marrow iron stores. If marrow iron stain is not available, the transferrin saturation must be \geq 20% or a serum ferritin \geq 100 ng/100 mL or soluble transferrin receptor $<$ 5mg/L.
8. Women must not be pregnant or breastfeeding. Females of childbearing potential should have 2 negative pregnancy tests (sensitivity of at least 50 mIU/mL). The

first test should be performed within 10-14 days, and the second test within 24 hours prior to prescribing lenalidomide.

9. Females of reproductive potential must adhere to the scheduled pregnancy testing as required in the Revlimid REMS® program. Able to take aspirin (81 or 325 mg) daily as prophylactic anticoagulation (patients intolerant to ASA may use warfarin or low molecular weight heparin).

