11 RESPONSE CRITERIA

MDS Response Criteria: Modified International MDS Working Group (IWG) Criteria for Measurement of Response/Treatment Effect in MDS (20) will be used to assess response.

Complete Remission (CR)

Bone marrow evaluation (>4 weeks): Bone marrow showing \leq 5% myeloblasts with normal maturation of all cell lines. When erythroid precursors constitute < 50% of bone marrow nucleated cells, the percent of blasts is based on all nucleated cells; when there are > 50% erythroid cells, the percent blasts should be based on the non-erythroid cells. This response should last for at least 4 weeks. Dysplasia if present will be noted.

Peripheral Blood Counts (Absolute values must last >4 weeks)

- o Hemoglobin greater than 11 g/dL (untransfused, patient not on erythropoietin).
- o Neutrophils 1000/mm³ or more (not on a myeloid growth factor)
- o Platelets 100 000/mm³ or more (not on a thrombopoietic agent)
- o Blasts – 0%
- o Hematologic improvement should be obtained.

Marrow CR: Bone marrow: < 5% myeloblasts and decrease by > 50% over pretreatment marrow. Peripheral blood: if hematologic improvement occurs, it will be noted in addition to marrow CR

Partial Remission (PR)

All of the CR criteria (if abnormal prior to treatment), except

- o Bone marrow evaluation: Blasts decreased by 50% over pretreatment, b

Stable Disease

Failure to achieve at least a PR, but with no evidence of progression for >8 weeks.

Failure

Death during treatment or disease progression characterized by worsening of cytopenias, increase in the percent of bone marrow blasts, or progression to an MDS FAB subtype more advanced than pretreatment.

Relapse (following a CR or PR)

One or more of the following:

- o Return to pretreatment bone marrow blast percentage.
- o Decrement of > 50% from maximum remission response levels in neutrophils or platelets.
- o RBC transfusion dependence (> 2 units RBC transfusions over an 8 week period) or a reduction in hemoglobin concentration by >1.5 g/dL in the absence of acute infection, gastrointestinal bleeding, hemolysis, treatment hiatus etc.

6. Disease Progression

A 50 % increase in blasts, depending on baseline blastpercent, if confirmed by subsequent BM examination (Fig 5).

- o For patients with < 5% blasts: increase to > 10% blasts
- o For patients with 5% to 10% blasts: > 50% increase to > 10% blasts
- o For patients with 10% to 20% blasts: > 50% increase to 20% blasts

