- o For patients with 20% to 30% blasts: > 50% increase to 30% blasts

Any of the following:

At least 50% decrement from maximum remission/response in granulocytes or platelets

Reduction in Hgb by 2 g/dL

Transfusion dependence

7. Disease Transformation

Transformation to AML (> 30% blasts).

Cytogenetic Response

Requires 20 analyzable metaphases when using conventional techniques. Analysis of data will require 20 metaphases before and after treatment. Fluorescent *in situ* hybridization (FISH) may be used as a supplement to follow a specifically defined cytogenetic abnormality, but it is not a substitute for conventional cytogenetic studies.

Cytogenetic response is defined as follows:

Complete response: Restoration of a normal karyotype in patients with a documented pre-existing clonal (>2 metaphases abnormal) chromosome abnormalities.

Partial response: > 50% reduction in the percentage of bone marrow metaphases with only clonal abnormality.

Hematologic Improvement

Improvements must last >8 consecutive weeks.

1. Erythroid Response

Hgb increase by 1.5 g/dL if not transfusion dependent Relevant reduction of units of RBC transfusions by an absolute number of at least 4 RBC transfusions/8 wk compared with the pretreatment transfusion number in the previous 8 wk. Only RBC transfusions given for a Hgb of 9.0 g/dL pretreatment will count in the RBC transfusion response evaluation

2. Platelet Response

For patients with a pretreatment count < 100,000/mm³, an absolute increase of > 30,000/mm³ (for patients with pretreatment counts >20,000).

For patients with pretreatment counts < 20,000, an increase to absolute count above 20,000 by at least 100% increase will be considered as response.

†;for platelet transfusion-dependent patients, stabilization of platelet counts and platelet transfusion independence.

3. Neutrophil Response

At least 100% increase and an absolute increase $> 0.5 \times 10^9/L$

4. Progression/Relapse Following Erythroid Hematologic Improvement

At least 1 of the following:

At least 50% decrement from maximum response levels in granulocytes or platelets

Reduction in Hgb by 1.5 g/dL

Transfusion dependence

Duration of Response

Time to disease progression (as per Bone Marrow Responses above) or progression/relapse following hematologic improvement (as per Hematologic Improvement above).

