14.2 Sample size and power considerations

The primary outcome is major erythroid response. A maximum of 52 patients will be enrolled into the study. An early stopping rule for lack of efficacy will be implemented as follows based on Simon's optimal two-stage design. After the first 25 patients have been enrolled and evaluated for response, the trial will be terminated early if fewer than 7 patients respond to treatment. If 7 or more responses are observed, the trial will continue until a total of 52 patients have been evaluated. At the end of the trial, the treatment will be considered efficacious and worthy of further study if 17 or more patients respond out of 52 patients.

The target response rate is assumed to be 40%. (Conservative estimate) A response rate less than 25% is considered to be clinically unimportant(21). Under these assumptions, the design specified above has the following operating characteristics. The probability of accepting the treatment for further study if the response rate is unacceptably low

(<25%) is at most 10%. In contrast, there is a 80% probability of accepting the treatment for further study if the response rate is at least 40%. The expected sample size is 32.4 subjects. It is also assumed that 10-20% of patients with plts > 50,000 that receive Len may not need Eltrombopag at all as there plts will not fall below 50,000.

Furthermore, since we will accrue patients with both high and low platelet counts, it is possible that the response rates to Lenalidomide will be different in these groups. These will be analyzed by exploratory studies.

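### The neutrophil rule and the hemoglobin-rise route in Section 11 carry no pretreatment condition, so a patient can score hematologic improvement in a lineage that was never low

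*Combined protocol and SAP*

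**What the plan says.** Section 11 lists three kinds of hematologic improvement, each lasting more than 8 weeks.

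- **Platelets.** The rule opens with a baseline condition: "For patients with a pretreatment count" below 100,000/mm3.
- **Erythroid, transfusion route.** A cut of at least 4 units per 8 weeks, with a pretreatment restriction: "Only RBC transfusions given for a Hgb of 9.0 g/dL pretreatment will count". The comparison sign is not visible in the text available to me.
- **Erythroid, hemoglobin route.** "Hgb increase by 1.5 g/dL if not transfusion dependent", with no pretreatment ceiling.
- **Neutrophils.** "At least 100% increase and an absolute increase" above 0.5 x 10^9/L, with no pretreatment ceiling.

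Inclusion item 4 (Section 6.1) requires hemoglobin of 10.0 g/dL or lower, or transfusion dependence. It then adds an alternative, "Or patients have platelet" counts below 50,000/uL with hemoglobin above 10.0 g/dL. No criterion in Sections 6.1 or 6.2 limits baseline neutrophils.

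Section 4.1.1 gives the primary efficacy objective as "To evaluate the rate of hematologic improvement of the eltrombopag/lenalidomide combination", with no lineage named, and the Synopsis lists hematologic improvement as the primary endpoint. Section 14.2, which holds the two-stage rule, says "The primary outcome is major erythroid response".

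**The concern.** Hematologic improvement is meant to record correction of a cytopenia. Section 11 follows that principle elsewhere: partial remission applies the CR criteria only where the value was abnormal before treatment. The neutrophil rule and the hemoglobin route break with it. Neutrophils rising from 2.0 to 4.1 x 10^9/L, or hemoglobin from 12.5 to 14.0 g/dL, for more than 8 weeks would each qualify.

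In a single-arm trial judged on a response count, such cases raise the reported rate without showing benefit. If they also feed the decision rule, they raise the chance of accepting an inactive treatment.

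**Working it through.** **1. Can a patient with no cytopenia in the lineage reach each rule?**

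| Rule | Pretreatment condition in Section 11 | Can a never-low patient score? |
|---|---|---|
| Platelets | below 100,000/mm3 | No |
| Transfusion route | pretreatment hemoglobin condition (9.0 g/dL) | No |
| Hemoglobin route | none | Yes, if enrolled by the platelet route of item 4 |
| Neutrophils | none | Yes, any patient with a normal count |

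**2. Check of the two examples.** Neutrophils: 4.1/2.0 = 2.05, a 105% increase, and 4.1 - 2.0 = 2.1, above 0.5. Hemoglobin: 14.0 - 12.5 = 1.5 g/dL. Both meet the written rules.

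**3. The plan's own operating characteristics.** Inputs from Section 14.2: 25 patients in stage 1, continue with 7 or more responders, success with 17 or more of 52, unacceptable rate 25%, target 40%. The formula is

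P(success) = sum over x = 7 to 25 of b(x; 25, p) x P[Bin(27, p) >= 17 - x].

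- Rule as written: 11.8% at p = 0.25, 85.6% at p = 0.40, expected size 36.9 at p = 0.25.
- Stated: at most 10%, 80%, and 32.4.
- Stopping at 7 or fewer of 25 (sum from x = 8): 9.9%, 80.0% and 32.4, which matches all three.

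This boundary mismatch is a separate matter. Both versions are shown below so that the illustration does not depend on it.

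**4. Illustration.** The share of spurious responses is not in the documents; 0 to 5 percentage points is an assumed range. The calculation also assumes that these responses count toward the rule. In 52 patients, 2 points is 0.02 x 52 = 1.04 responders and 5 points is 2.6.

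| Points added to a true 25% | p used | Rule as written | Stop at 7 or fewer of 25 |
|---|---|---|---|
| 0 | 0.25 | 11.8% | 9.9% |
| 2 | 0.27 | 19.6% | 16.7% |
| 5 | 0.30 | 35.2% | 30.5% |

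If the miscount instead affects a share s of true non-responders, p = 0.25 + 0.75s. Then s = 2% gives p = 0.265 and 17.5% (14.8% with the other boundary), and s = 5% gives p = 0.2875 and 28.3% (24.3%).

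**5. Candidate cutoffs in the protocol disagree.** The CR criteria in Section 11 use "Hemoglobin greater than 11 g/dL" and neutrophils of at least 1,000/mm3. The IPSS table in Appendix 4 counts a cytopenia at hemoglobin below 10 g/dL and neutrophils below 1,800/uL. A patient with neutrophils of 1,000 to 1,799 is low by Appendix 4 but not by the CR value. A non-transfused patient with hemoglobin from 10 to 11 g/dL is low by the CR value but not by Appendix 4.

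**The case against.** **The decision rule may not be touched.** The 7/25 and 17/52 limits sit under major erythroid response, so on that reading a neutrophil-only response adds nothing to them. This stands, and it removes the neutrophil route from the error calculation unless hematologic improvement is the endpoint tested. It does not close the hemoglobin route. Section 11 does not define major erythroid response. The only description, in Section 3.4 for an earlier study, includes a hemoglobin rise above 2 g/dL with no baseline ceiling. The 12.5 to 14.0 example would fail that, but a larger rise from a similar start would not.

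**The exposed group may be small.** Only patients enrolled by the platelet route can be non-anemic, and some of them may count validly through platelets. Section 8.1.2 withholds lenalidomide above 14 g/dL, so anyone starting above 12.5 must enter the hold range to score. Section 3.4 reports dose-limiting neutropenia in 67% of patients in an earlier lenalidomide study, so a sustained doubling from normal runs against the expected effect. All of this is fair: the frequency could be near zero.

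**The cited criteria may supply the conditions.** Section 11 adopts the published modified IWG criteria, and the Synopsis refers to IWG 2006. Their content is not in the documents, so this cannot be checked. Section 11 nevertheless writes out some baseline conditions and not others, and a site scoring from it would apply what is printed.

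**Stronger inferences.** A reader might infer that platelets alone carry a baseline condition; the transfusion route has one too. A reader might also infer that spurious responders certainly enter the 17/52 count, or that the false-positive rate is 35%. The conflict over the primary endpoint leaves the former open, and the latter rests on an assumed share.

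**Conclusion.** The gap is real and should be closed before responses are scored. Two of the four routes to hematologic improvement lack a pretreatment condition, eligibility does not supply one, and the Synopsis and Section 4 make improvement in any lineage primary.

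The size is unknown. The hemoglobin route is confined to patients enrolled with platelets below 50,000/uL and hemoglobin above 10 g/dL, a group whose number is not given; the neutrophil route is open to anyone with a normal count. The figures above show only that the two-stage rule is sensitive: about one extra responder in 52 moves the error at a true 25% from 11.8% to 19.6% (9.9% to 16.7% with the higher stage-1 boundary), if that responder counts. They are not an estimate of this trial's error rate.

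**What to change.** 1. In Section 11, add a pretreatment condition to the neutrophil rule and to the hemoglobin route. Take it from the adopted modified IWG criteria and check it against the protocol's own values: 11 g/dL and 1,000/mm3 in the CR criteria, 10 g/dL and 1,800/uL in Appendix 4. State which applies and why; the CR values are response targets and should not be adopted by default.
2. Count a response only in a lineage that was low at baseline, and report each lineage's rate among patients low in that lineage.
3. Name one primary endpoint in the Synopsis, Section 4 and Section 14.2. If it is major erythroid response, define it in Section 11. Until this is settled, the added conditions have no defined effect on the decision rule.

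The cost is a few phrases. Baseline blood counts and transfusion history are already in the schedule of assessments, so no new data are needed. The downside is that the reported response rate may fall slightly.

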5 INVESTIGATIONAL PLAN

5.1 Overall design

This is a multicenter, Phase II study evaluating the efficacy and safety of the combination of lenalidomide and eltrombopag in low risk MDS. This study will include patients with low risk MDS (IPSS low and Int-1) with symptomatic anemia or transfusion dependence. Patients will be treated in 2 separate arms based on their baseline platelet counts:

Arm A : Patients with platelet counts $\geq 50k$ at baseline:

These patients will start Len at 10mg/d for 3 weeks/month, and will not start Eltrombopag until the platelet counts drop below 50,000. If platelets drop less than 50,000, Len will be stopped and Eltrombopag will be started at a dose of 100mg initially and titrated up (similar schema to 509 study) to achieve a platelet count above 50,000. Once the platelet count above 50,000 is achieved, the same dose of Eltrombopag will be continued for an additional two weeks. Once a platelet count $> 50,000$ is maintained for two weeks, Eltrombopag will be discontinued and Len will be started as a single agent. If the plts again fall below 50k then Len will be stopped and Eltrombopag will be re-initiated at the dose that was last given to the patient. Once the platelets are increased to above 50,000 and maintained at this level for 2 weeks, Len will be started again and this time will be given concurrently with Eltrombopag. These agents will now be used concurrently for all subsequent cycles.

Arm B: Patients with Plts $< 50k$ at baseline

These patients will not receive Len initially. Eltrombopag will be started alone at a dose of 100mg initially and titrated up (similar schema to 509 study) to achieve a

platelet count above 50,000. Once the platelet count above 50,000 is achieved, the same dose of eltrombopag will be continued to additional two weeks. Once the plt count > 50,000 is maintained for two weeks, the patients will discontinue eltrombopag and follow the treatment algorithm described for patients in arm A. Patients that never drop their platelet counts below 50,000 will not receive any additional eltrombopag. (Figure 1)

Treatment with myeloid growth factors is permitted for the management of neutropenia at the discretion of the treating investigator.

Study drugs will be continued until disease progression or unacceptable toxicities.

Bone marrow examinations will be performed at baseline, at every 4 months and at study discontinuation.

52 evaluable adult subjects with MDS will be evaluated.

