Mineral supplements (such as calcium, magnesium, aluminium, zinc, selenium or iron) are permitted during the study but study medication must be taken at least 4 hours before and 4 hours after consumption of these supplements. Similarly, eltrombopag must be taken at least 4 hours before and 4 hours after consumption of dairy products (such as milk, yogurt, and cheese).

HMG-CoA Reductase Inhibitors (statins)

Subjects will be permitted to use HMG-CoA reductase (3-hydroxy-3-methyl-glutaryl-CoA) inhibitors during the study, but these drugs should be used with caution and a 50% dose reduction of the HMG-CoA reductase inhibitor is recommended, with close monitoring for safety, such as liver chemistry and signs and symptoms of myolysis, and efficacy, such as cholesterol and triglycerides (refer to individual product information for monitoring recommendations).

Preclinical data showed that eltrombopag is an inhibitor of the transporters OATP1B1 and BCRP. Therefore, a clinical drug interaction study to evaluate the impact of eltrombopag on the PK of rosuvastatin, an OATP1B1 and BCRP substrate, was conducted in healthy subjects. Co-administration of eltrombopag 75 mg once daily for 5 days with a single 10mg dose of rosuvastatin administered on Day 5 increased plasma rosuvastatin C_{max} 2.03-fold and AUC(0-∞) 55%. Concomitant administration of eltrombopag and other OATP1B1 or BCRP substrates should be used with caution.

Concomitant MDS Therapy

G-CSF is allowed during the study for subjects with severe neutropenia and recurrent infections. Subjects who enter the study on G-CSF should continue at the same dose schedule until the optimal dose of study medication has been established.

Any change in dosage of any concomitant medication (change in dose or frequency) MUST be recorded in the eCRF, to include: drug name, dose, frequency of administration, start and stop dates and indication.

Prohibited Medications and Non-Drug Therapies

Subjects must abstain from using prohibited prescription or non-prescription drugs within 7 days or 5 half-lives (whichever is longer) prior to the first dose of study

medication until completion of follow-up procedures (Section 5.3, Exclusion Criteria).

The following medications are prohibited during the study:

- Any other TPO-R agonists

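### Neutrophil improvement in Section 11 carries no off-growth-factor condition, so a sustained G-CSF effect can be scored as hematologic improvement

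*Combined protocol and SAP*

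**What the plan says.** Sections 1 and 4.1.1 give the first primary objective as "To evaluate the rate of hematologic improvement of the eltrombopag/lenalidomide combination", with no lineage named, and the synopsis lists hematologic improvement as the primary endpoint. Section 14.2 instead names major erythroid response as the primary outcome and attaches the two-stage rule to it.

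Section 11 splits hematologic improvement into erythroid, platelet and neutrophil response. The neutrophil part reads "At least 100% increase and an absolute increase" of more than 0.5 × 10⁹/L. The one condition common to all three is "Improvements must last >8 consecutive weeks". The neutrophil part contains nothing about growth factor and no baseline limit. Under complete remission, the same section requires "Neutrophils 1000/mm³ or more (not on a myeloid growth factor").

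Growth factor use is expected on study:

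- Section 5.1: "Treatment with myeloid growth factors is permitted for the management of neutropenia at the discretion of the treating investigator".
- Section 8.5: "G-CSF is allowed during the study for subjects with severe neutropenia and recurrent infections", and "Subjects who enter the study on G-CSF should continue at the same dose schedule until the optimal dose of study medication has been established".
- Section 8.1.2 holds lenalidomide for a low neutrophil count only when growth factor has failed to correct it.

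Section 8.5 has concomitant medications, with start and stop dates, recorded in the eCRF. No section connects that record to the scoring of response.

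**The concern.** In a single-treatment study no control group absorbs the effect of supportive care. G-CSF exists to raise neutrophils, so a patient kept on it can meet the neutrophil definition whether or not lenalidomide or eltrombopag did anything. The complete remission criteria show that the authors saw this problem, but they did not carry the condition over to hematologic improvement, which the objectives make primary. Because Section 5.1 leaves use to the investigator, the contamination could also vary by site.

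At stake are the reported neutrophil and any-lineage improvement rates and the secondary outcomes of time to and duration of improvement. On one reading of the primary endpoint, the conclusion of the trial is at stake too.

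**Working it through.** **1. Is the condition supplied elsewhere?** Compare the two neutrophil criteria in Section 11.

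| | Complete remission | Hematologic improvement |
|---|---|---|
| Threshold | 1000/mm³ or more | at least doubled, and a rise above 0.5 × 10⁹/L |
| Minimum duration | more than 4 weeks | more than 8 weeks |
| Off growth factor | required | not mentioned |

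The instruction in Section 8.5 to hold the G-CSF schedule constant covers only patients who enter on it, and only until the study drug dose is settled. It does not reach G-CSF started on study or changed later. The gap is not closed.

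**2. Effect on the reported rate.** The documents give no frequency for neutrophil responses due to G-CSF alone. Let g be the share of patients, among those who would otherwise not respond, who score only through G-CSF. With a true any-lineage rate of 25% (the uninteresting rate in Section 14.2, used here for illustration), the observed rate is

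p = 0.25 + 0.75 × g

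For example, g = 5% gives 0.25 + 0.75 × 0.05 = 0.2875.

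**3. The plan's own operating characteristics.** Section 14.2 states a first stage of 25, stopping with fewer than 7 responses, success at 17 or more of 52, rates of 25% and 40%, error at most 10%, power 80% and expected size 32.4. The exact probability of success is

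Σ over x ≥ c of P(X₁ = x) × P(X₂ ≥ 17 − x), with X₁ ~ Bin(25, p), X₂ ~ Bin(27, p) and c the smallest first-stage count that continues.

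- Rule as written (c = 7): error 11.8%, power 85.6%, expected size 36.9. The stated figures are not reproduced.
- Stopping at 7 or fewer (c = 8): error 9.9%, power 80.0%, expected size 32.4. The stated figures are reproduced.

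The one-response discrepancy in the boundary is a separate matter. Both versions are carried forward.

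**4. Effect on the decision, only if any-lineage improvement is what the rule counts.**

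| g (assumed) | Observed rate at a true 25% | Chance of success, rule as written | Chance of success, stop at 7 or fewer |
|---|---|---|---|
| 0 | 25.0% | 11.8% | 9.9% |
| 1% | 25.8% | 14.5% | 12.2% |
| 2% | 26.5% | 17.5% | 14.8% |
| 5% | 28.8% | 28.3% | 24.3% |
| 10% | 32.5% | 49.9% | 44.1% |

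If the rule counts major erythroid response, neutrophil scoring does not enter it. The last two columns then stay at their g = 0 values.

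**5. Direction.** A patient whose baseline count was taken on G-CSF starts from a raised level, so doubling is harder and a true response can be missed. Section 11 also counts a fall of at least 50% in granulocytes from their maximum as progression or relapse, including after erythroid improvement. A peak on G-CSF raises that maximum, so stopping G-CSF can end a recorded response early.

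**The case against.** A reader might infer that the trial's false-positive rate is inflated to 28% or 50%. The documents do not support that as a general statement. The 25% and 40% rates and the 17-of-52 boundary belong to Section 14.2, which names an erythroid outcome. Those figures need two further assumptions: that any-lineage improvement is counted, and that g is as high as 5% or 10%.

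There are reasons to think g is small:

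- Entry under Section 6.1 is through anemia, transfusion dependence or low platelets, not neutropenia.
- Section 8.5 describes a narrower indication for G-CSF than Section 5.1.
- Lenalidomide lowers neutrophils (Section 3.4 reports 67% with dose-limiting neutropenia in an earlier study), so G-CSF may only restore a fallen count. Scoring requires a doubling from the pretreatment level for more than 8 weeks.
- G-CSF adds a responder to the any-lineage rate only if that patient has no erythroid or platelet improvement.

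All of this stands as a limit on size, and it is why the range starts at zero. None of it supplies the missing condition.

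A reader might also infer that the bias is always upward. It is not, for the reasons in step 5 of the working.

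Finally, Section 11 adopts published working-group criteria that are not reproduced in full. Whether they carry a growth-factor condition cannot be checked here. The protocol writes out its own criteria, and those are silent. If the source has the condition, stating it costs nothing.

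**Conclusion.** The point holds as a gap in the scoring rule. As Section 11 stands, a neutrophil rise sustained for more than 8 weeks on G-CSF is a hematologic improvement. The likely result is an inflated neutrophil rate and, to a smaller degree, an inflated any-lineage rate: 0.75 to 7.5 percentage points for g between 1% and 10% at a true 25%, where g is assumed and could be close to zero. Time to and duration of improvement are also affected, and patients who enter on G-CSF may be biased downward.

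The consequence for the go/no-go decision depends on a conflict that the protocol must resolve, namely hematologic improvement (Sections 1 and 4.1.1) against major erythroid response (Section 14.2). Under the second there is no effect on the decision. Under the first, the chance of success at a true 25% rises as tabulated. The change is worth making under either reading, because improvement rates will be reported in both cases.

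**What to change.** Add to the hematologic improvement part of Section 11, as a scoring rule that leaves G-CSF use itself unchanged:

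- Neutrophil counts taken on a myeloid growth factor, or within a prespecified washout after it, do not count toward neutrophil response, toward the baseline from which response is measured, or toward the maximum used for the 50% granulocyte decrement.
- The improvement of more than 8 weeks must be met on counts taken off growth factor. A patient given G-CSF at some other time is not excluded by that fact alone.
- Improvement is reported by lineage as well as overall.

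The length of the washout must be fixed before response is scored. State in the same amendment which outcome the 17-of-52 rule counts.

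The cost is a short paragraph in Section 11 and its programming. The G-CSF dates needed are already collected under Section 8.5, and no sample-size figure changes. The reported improvement rate may be slightly lower, and some patients, chiefly those with no baseline count off G-CSF, may be unevaluable for neutrophil response. Their number should be reported.
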